## LIST OF ABBREVIATIONS AND DEFINITION OF TERMS

ADA:	anti-drug antibody
ATC:	anatomic category
BOR:	best overall response
CA:	cytogenetic abnormality
CI:	confidence interval
CR:	complete response
DOR:	duration of response
ECOG:	Eastern Cooperative Oncology Group
eCRF:	electronic case report form
EORTC:	European Organization for Research and Treatment of Cancer
EQ:	EuroQol
FLC:	free light chain
HLGT:	high level group term
HLT:	high-level term
HR:	hazard ratio
IAT:	indirect antiglobuline test
IMP:	Investigational Medicinal Product
IMWG:	International Myeloma Working Group
IPd:	isatuximab pomalidomide dexamethasone
IRC:	independent response committee
IRT:	interactive response technology
ISS:	international staging system
ITT:	intent to treat
LDH:	lactate dehydrogenase
MedDRA:	Medical Dictionary of Regulatory Activities
MM:	multiple myeloma
MR:	minimal response
MRD:	minimal residual rate
MY:	myeloma specific module
NE:	non-evaluable
ORR:	objective response rate
OS:	overall survival
PCSA:	potentially clinically significant abnormality
Pd:	pomalidomide dexamethasone
PD:	progressive disease
PFS:	progression free survival
PK:	pharmacokinetic
PR:	partial response
PS:	performance status
PT:	preferred term, prothrombin time
QLQ:	quality of life questionnaire

R-ISS:	revised international staging system
RS:	raw score
SOC:	system organ class
TEAE:	treatment-emergent adverse event
TT1R:	time to first response
TTBR:	time to best response
VAS:	visual analogue scale
VGPR:	very good partial response
WHO-DD:	World Health Organization-Drug Dictionary

# 1 OVERVIEW AND INVESTIGATIONAL PLAN

## 1.1 STUDY DESIGN AND RANDOMIZATION

This is a prospective, multicenter, multinational, randomized, open-label, parallel group and 2-arm study evaluating the clinical benefit of isatuximab in combination with pomalidomide and low-dose dexamethasone as compared to pomalidomide and low-dose dexamethasone for the treatment of patients with refractory or relapsed and refractory multiple myeloma who have received at least two lines of therapy including lenalidomide and a proteasome inhibitor (bortezomib, carfilzomib or ixazomib) alone or in combination and have demonstrated disease progression on or within 60 days of completion of the last therapy.

After confirmation of eligibility criteria, patients will be randomly assigned, using an interactive response technology (IRT), in a 1:1 ratio to one of the two arms:

- Isatuximab in combination with pomalidomide and low dose dexamethasone (IPd, experimental arm).
- Pomalidomide and low-dose dexamethasone (Pd, control arm).

The duration of the study for a patient will include a period for screening of up to 3 weeks. The cycle duration is 28 days. Patients will continue study treatment until disease progression, unacceptable toxicity, patient wish, or any other reason, whichever comes first.

Randomization will be stratified according to:

- Age (<75 years versus  $\geq 75$  years).
- Number of previous lines of therapy (2 or 3 versus >3).

Approximately 300 patients (150 patients per arm) will be randomized from approximately 140 sites. Patient enrollment will be stopped after progression free survival (PFS) analysis or when 300 patients will have been randomized, whichever is first.

## 1.2 OBJECTIVES

### 1.2.1 Primary objectives

The primary objective of this study is to demonstrate the benefit of IPd arm in the prolongation of PFS as compared to Pd arm in patients with refractory or relapsed and refractory multiple myeloma.

### 1.2.2 Secondary objectives

The key secondary objectives are:

- To evaluate the ORR as per IMWG criteria in each arm.
- To compare the OS between the 2 arms.

The other secondary objectives are:

- To evaluate the Time to Progression (TTP) in each arm.
- To evaluate the PFS in high risk cytogenetic population defined as patients carrying del(17p), t(4;14), t(14;16) in each arm.
- To evaluate the Duration of Response (DOR) in each arm.
- To evaluate the safety of the combination of IPd versus that of Pd in both treatment arms.
- To determine the pharmacokinetic (PK) profile of isatuximab in combination with pomalidomide.
- To evaluate the immunogenicity of isatuximab.
- To assess disease-specific and generic health-related quality of life (HRQL), disease and treatment-related symptoms, health state utility and health status.

### 1.2.3 Exploratory objectives

The exploratory objectives are:

- To explore the relationship between immune genetic determinants and efficacy endpoints.
- To explore pharmacokinetics (PK) and pharmacodynamic (PDy) relationships.
- To explore the minimal residual disease (MRD) rate in both treatment arms.

### 1.3 DETERMINATION OF SAMPLE SIZE

The sample size calculation is based on the primary efficacy endpoint (ie, PFS). The following assumptions were used:

- Pd arm has a median PFS of 4.0 months.
- IPd arm will have 40% risk reduction in hazard rate in comparison to Pd arm. The targeted hazard ratio is 0.60, which corresponds to an improvement in the true median progression free survival time from 4 months to 6.67 months.
- A log-rank test at a one-sided 2.5% significance level.

Based on the above assumptions, a total of 162 PFS events are needed to achieve a 90% power for the study.

Objective for OS also support the sample size calculation using the following assumptions:

- Pd arm has a median OS of 13.0 months.
- IPd will have 31.5% risk reduction in hazard rate in comparison to Pd arm. The targeted hazard ratio is 0.685 and this is expected to correspond to a difference of 6 months in median OS between the control arm and the experimental arm.
- A log-rank test at a one-sided 2.5% significance level.

- An interim analysis for efficacy assessment on OS is planned at the time of primary analysis on PFS which is estimated to occur when about 36% of the OS events will be observed. An O'Brien and Fleming  $\alpha$ -spending function will be used to obtain the nominal significance levels for the interim and final analyses of survival.

Based on the above assumptions, a total of 220 deaths are needed to achieve 80% power for the study.

Approximately 300 patients (150 in each arm) would be adequate to achieve the targeted number of events for both PFS and OS. After the PFS analysis, no additional patient will be randomized and OS analysis will be performed on the number of patients already randomized.

#### 1.4 STUDY PLAN

The complete study plan is presented in Section 1.1 of the protocol.

#### 1.5 MODIFICATIONS TO THE STATISTICAL SECTION OF THE PROTOCOL

Two changes were made from the protocol to the SAP version 1 (approved on 06-APR-2017)

- The population flag for PRO has been removed and the analysis population has been clarified in the section 2.4.9 (analyses of quality of life/health economics variables)
- A biomarker population was added for biomarker analyses

#### 1.6 STATISTICAL MODIFICATIONS MADE IN THE STATISTICAL ANALYSIS PLAN

The statistical analysis plan history table below gives the timing, rationale, and key details for major changes to the statistical analysis features in the amended statistical analysis plan.

**Table 1 - Statistical analysis plan statistical changes**

SAP version number	Date approved	Rationale	Description of statistical changes
3	20-Oct-2020	An amendment (Amendment 6) to the protocol was issued after the primary analysis to add a second interim analysis for OS. The current version of SAP is consistent with this protocol amendment.	An interim analysis has been added at approximately 90% of events. The boundaries for final analysis were updated.
3	20-Oct-2020	To further evaluate the impact of study treatments on subsequent therapies	The following analyses have been added: 
 
- Analysis of PFS2 as per investigator
 
- Summary of further anti-myeloma treatments by drug class and by number of lines
 

SAP version number	Date approved	Rationale	Description of statistical changes
			
 
- ORR, VGPR rate and CR rate on subsequent therapy by number of subsequent line and selected drug class or agent
 
- PFS on first line of further therapy (based on investigator assessment)
 

3	20-Oct-2020	One analysis was added to better characterize the cytogenetic profile of patients	Summary of gain(1q21) abnormality at baseline
3	20-Oct-2020	Clarification	Definition of R-ISS stage was clarified
3	20-Oct-2020	One analysis was added to identify the TEAEs related to COVID19	Summary of COVID19 related TEAEs
3	20-Oct-2020	Some analyses were planned only for the primary analysis or will not be provided at time of second interim and final OS analyses because not deemed relevant at this stage of the study	A table describing analyses that will be provided at time of primary analysis of PFS and second interim and final OS analyses has been added in section 3.
2	07-Nov-2018	Safety analyses were added to better characterize the safety profile and to account for FDA comments on the submission strategy	
The following analyses have been added:
 
 
- Cumulative exposure to treatment in patient-years
 
- Isatuximab dose reductions
 
- Infusions without IR medication
 
- Exposure-adjusted analyses of TEAEs
 
- Indirect antiglobulin test
 
- Neutropenic complications
 
- Thrombocytopenia and haemorrhages
 
- Hemolytic disorders
 
- Autoimmune disorders
 

2	07-Nov-2018	Sensitivity analyses for PFS and OS were added to further evaluate the efficacy of study treatments	
The following sensitivity analyses have been added:
 
 
- Analysis of PFS as per investigator assessment, ignoring symptomatic deterioration has been added
 
- Analysis adjusting OS for switch to subsequent anti-cancer treatment therapy
 

SAP version number	Date approved	Rationale	Description of statistical changes
2	07-Nov-2018	Additional exploratory endpoints were added to further characterize the efficacy of study treatments	The following analyses have been added: 
 
- Time to first response
 
- Time to best response
 
- Overall response rate based on investigator assessment
 
- Proportion of patients with VGPR or better as best overall response
 

2	07-Nov-2018	Subgroup analyses were added to further evaluate the efficacy in specific subgroups	The following subgroup analyses have been added: 
 
- Age as per eCRF
 
- Regulatory region
 
- Refractory to lenalidomide
 

2	07-Nov-2018	Some subgroup variables were removed because not deemed relevant based on number of patients and/or further clinical evaluation	The following subgroup analyses have been removed: 
 
- Age per IRT
 
- Previous allogeneic transplantation
 
- Previous therapy with anti-CD38 mAb
 
- Existing plasmacytomas
 
- Refractory to lenalidomide in last previous regimen
 
- Refractory to IMiD
 

2	07-Nov-2018	Based on clinical consideration, death due to PD occurring within 45 days after first documentation of PD were used to confirm PD (including death occurring after initiation of further therapy)	
 
- Death due to PD occurring within 45 days after a first documentation of PD based on M-protein is considered as confirmation of PD
 

2	07-Nov-2018	The following data handling conventions were added to account for cases not described in the previous version of the SAP and that were reported in the database	The following conventions have been added: 
 
- Patients who received only one prior therapy will be classified in the "2 or 3 prior lines" stratum as per eCRF.
 
- Convention for missing/partial death dates
 

SAP version number	Date approved	Rationale	Description of statistical changes
2	07-Nov-2018	To clarify some definitions and analyses	
The following definitions have been updated:
 
 
- Baseline value
 
- Intolerance to lenalidomide and/or PI
 
- Overall number of cycles started
 
- Isatuximab infusion interruption
 
- Planned dose intensity of pomalidomide
 
- Persistent and indeterminate ADA
 
 
The following analyses have been updated:
 
 
- Evaluation of confounding for primary analysis (following FDA comment)
 
- Analysis of cytogenetic abnormalities
 
- Analysis of MRD
 
- Analysis of PK parameters
 
- Analyses of ePRO
 

2	07-Nov-2018	Due to issues in data collection	Removal of analysis of thyroid function parameters

## 2 STATISTICAL AND ANALYTICAL PROCEDURES

### 2.1 ANALYSIS ENDPOINTS

#### 2.1.1 Demographic and baseline characteristics

The baseline value is defined as the last value or measurement taken up to the date and time of the first dose of study treatment. For efficacy laboratory parameters (eg, serum and urine M-protein), unscheduled assessment performed on the date of first study treatment administration (Cycle 1 Day 1) will be considered as baseline value; for other laboratory tests, unscheduled assessment performed on the date of first study treatment administration will be considered as post baseline. For patients randomized and not treated, the baseline value is defined as the last available value obtained up to the date and time of randomization.

All baseline safety and efficacy parameters (apart from those listed below) are presented along with summary statistics in the safety and efficacy sections ([Section 2.4.5](#) and [Section 2.4.4](#)).

#### *Demographic characteristics*

Demographic variables include gender (Male, Female), race (White, Black, Asian, American Indian/Alaska Native, Native Hawaiian/Other Pacific Islander, Not reported, Unknown), ethnicity (Hispanic or Latino, Not Hispanic or Latino, Not reported, Unknown), geographical region (Eastern Europe, Western Europe, North America, Asia, Other countries, see definition in [Appendix G](#)), regulatory region (Western countries, Other countries, see definition in [Appendix G](#)), age in years (quantitative and qualitative variables : <65, [65 - 75[ and ≥75 years), weight (kg), and eastern cooperative oncology group (ECOG) performance status (PS) at baseline.

#### *Medical or surgical history*

Medical or surgical history includes relevant history of previous or associated pathologies other than multiple myeloma including respiratory function history and smoking status.

This information will be coded using the Medical Dictionary for Regulatory Activities (MedDRA) version 21.0 or higher. Respiratory function history will be analyzed using two groupings (see details in [Section 2.1.4.1](#)).

#### *MM characteristics at diagnosis*

The following multiple myeloma characteristics at initial diagnosis will be described:

- Time from initial diagnosis of MM to randomization (in years).
- ISS stage (as collected in eCRF).
- MM type: heavy and light chain component (as collected in eCRF).
- Bi-clonal status (as collected in eCRF).

### ***MM characteristics at study entry***

The following MM characteristics at study entry will be described:

- ISS stage (see definition in [Table 2](#)),  $\beta$ 2-microglobulin level in mg/L (quantitative results and by category : <3.5 mg/L, [3.5-5.5 mg/L[ and  $\geq$ 5.5 mg/L), albumin in g/L (quantitative results and by category: <35 g/L and  $\geq$ 35 g/L).
- Revised ISS (see definition in R-ISS, [Table 3](#)), serum LDH ( $\leq$ ULN, >ULN) and cytogenetic abnormality (CA).
- Cytogenetic abnormalities from central FISH assessment:
  - Number and percentage of patients with cytogenetic abnormality for del(17p), t(4;14), and t(14;16). Abnormality is defined as at least 30% of abnormal plasma cells for t(4;14), and t(14;16), and at least 50% of abnormal plasma cells for del(17p)
  - Type of risk: Standard risk, high-risk (defined as presence of del(17p) and /or translocation t(4;14) and /or translocation t(14;16) abnormality) and unknown/missing
  - Number of patients with 2 abnormalities: del(17p) and t(4,14); and, del(17p) and t(14,16)
- Gain(1q21) abnormality. Abnormality is considered positive if present in at least 30% of analyzed plasma cells. Isolated gain(1q21), defined as gain(1q21) abnormality and otherwise standard-risk cytogenetics will also be summarized.
- MM type: Heavy and light chain components (as collected in eCRF).
- Bi-clonal status (as collected in eCRF).
- Refractory status
  - Relapsed and refractory: non-responsive while on salvage therapy or progresses within 60 days of last therapy in patients who have achieved minimal response or better at some point previously before then progressing in their disease course,
  - Primary refractory: never achieve MR or better in any prior therapies,
  - Relapse: all cases not meeting the relapse and refractory or primary refractory definition.
- Measurable paraprotein at baseline (according to central laboratory) ([Table 4](#)),
- % of plasma cells in bone marrow at baseline (quantitative and qualitative variables: 0%, ]0-5%[, [5-20%[, [20-50%[ and  $\geq$ 50%),
- Patients with plasmacytoma (as per investigator and IRC),
- Patients with bone lesions and number of lesions (as per investigator and IRC)

**Table 2 - ISS staging definition**

Stage	Definition
Stage I	$\beta$ 2-microglobulin <3.5 mg/L and albumin $\geq$ 35 g/L
Stage II	[[ $\beta$ 2-microglobulin <3.5 mg/L and albumin <35 g/L] or [ $\beta$ 2-microglobulin 3.5 - <5.5 mg/L]
Stage III	$\beta$ 2-microglobulin $\geq$ 5.5 mg/L

**Table 3 - R-ISS staging definition**

Stage	Definition
Stage I	$\beta$ 2-microglobulin <3.5 mg/L and albumin $\geq$ 35 g/L and no high-risk CA and LDH $\leq$ ULN
Stage II	Not R-ISS stage I or III
Stage III	$\beta$ 2-microglobulin $\geq$ 5.5 mg/L and either high-risk CA by iFISH or LDH >ULN
Not classified	Inconclusive iFISH unless stage III can be determined on LDH and $\beta$ 2 microglobulin only

High-risk CA by iFISH: Presence of del(17p) and /or translocation t(4;14) and /or translocation t(14;16)

CA: Cytogenetic abnormalities

iFISH: interphase fluorescent in situ hybridization

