**2.4.4.1.2 Subgroup analyses**

**Evaluation of Consistency:**

The consistency of the results from the primary analysis will be evaluated across pre-defined subgroups in patients with available results. The definition of each subgroup is defined in [Table 9](#). Depending upon the study results, additional subgroups may be examined, and subgroups with small sample sizes may be pooled to create a larger meaningful subgroup. For each subgroup, the treatment effect HR and its associated 95% confidence interval will be estimated. A forest plot summarizing the results for each subgroup will be provided.

For each pre-defined factor among the demographic/baseline characteristics defined in [Table 9](#), PFS will be analyzed using a Cox proportional hazards model with terms for the factor, treatment and their interaction. The test of the interaction will be performed at the 10% alpha level.

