**Table 9 - PFS subgroup analyses: covariates investigated**

Prognostic factor	Description
Age (eCRF)	<65 vs [65 - 75[ vs ≥75 years
Number of previous lines of therapy (IRT)	(2 or 3) vs >3
Gender	Male vs female
Race	Caucasian vs Asian vs other
Region of the world (geographical)	Western Europe vs Eastern Europe vs North America vs Asia vs Other countries
Region of the world (regulatory)	Western countries vs Other countries
ECOG PS at baseline	0 or 1 vs 2
ISS staging at study entry	I vs II vs III
R-ISS staging at study entry	I vs II vs III
Cytogenetic abnormality (del(17p), t(4;14), t(14;16))	At least one vs. none
Cytogenetic abnormality del(17p)	Yes vs No
MM type at diagnosis	IgG vs non IgG
Baseline creatinine clearance (MDRD formula)	>60 ml/min vs ≤60 ml/min
Refractory to PI	Yes vs No
Refractory to lenalidomide	Yes vs No

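### SAP Table 3 leaves patients with inconclusive iFISH without an R-ISS stage even where beta-2-microglobulin, albumin and LDH already fix the stage as II

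*SAP*

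**What the plan says.** SAP section 2.1.1, Table 3, defines R-ISS at study entry in four rows.

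- Stage I needs all of: beta-2-microglobulin <3.5 mg/L, albumin ≥35 g/L, LDH ≤ULN and no high-risk cytogenetic abnormality (CA).
- Stage III needs beta-2-microglobulin ≥5.5 mg/L "and either high-risk CA by iFISH or LDH >ULN".
- Stage II is the remainder: "Not R-ISS stage I or III".
- Not classified is: "Inconclusive iFISH unless stage III can be determined on LDH" and beta-2-microglobulin.

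R-ISS is then used as a factor. Table 9 lists "R-ISS staging at study entry" with three levels, I vs II vs III. SAP section 2.4.4.1.2 says that consistency is "evaluated across pre-defined subgroups in patients with available results", and that each factor gets a Cox model with a treatment interaction: "The test of the interaction will be performed at the 10% alpha level". The same factors are candidates in the stepwise prognostic model described under evaluation of confounding. Under section 2.4.4.2 they may also be used for subgroup analyses of the key secondary endpoints, which include OS.

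SAP Table 1 records, for version 3 dated 20-Oct-2020: "Definition of R-ISS stage was clarified".

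**The concern.** The last row accepts that a stage can be assigned without a conclusive iFISH when the laboratory values settle it, but applies this to Stage III only. Some patients with inconclusive iFISH cannot be Stage I or Stage III under any cytogenetic result. They meet the Stage II row and the Not classified row at once, so the table contradicts itself and programmers could resolve it either way.

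If the last row prevails, patients whose stage is logically certain are left out of one planned subgroup factor, its interaction test and the prognostic screen. Those parts of the plan already have few patients per level.

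**Working it through.** There is no figure in the plan to reproduce, because this is a classification rule. The inputs are the cut-points in SAP Table 3. Cross three levels of beta-2-microglobulin, two of albumin and two of LDH: 3 × 2 × 2 = 12 laboratory combinations. For each, apply the Stage I, II and III rows with high-risk CA absent and then present, and compare the result with the last row.

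| Beta-2-microglobulin (mg/L) | Albumin (g/L) | LDH | Combinations | Stage, CA absent | Stage, CA present | Table 3 if iFISH inconclusive |
|---|---|---|---|---|---|---|
| <3.5 | ≥35 | ≤ULN | 1 | I | II | Not classified |
| <3.5 | ≥35 | >ULN | 1 | II | II | Not classified |
| <3.5 | <35 | either | 2 | II | II | Not classified |
| 3.5 to <5.5 | either | either | 4 | II | II | Not classified |
| ≥5.5 | either | ≤ULN | 2 | II | III | Not classified |
| ≥5.5 | either | >ULN | 2 | III | III | III |

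- Unclassified under the last row: 1 + 1 + 2 + 4 + 2 = 10 of 12.
- Of these, Stage II under either iFISH result: 1 + 2 + 4 = 7.
- Of these, truly dependent on iFISH: 1 + 2 = 3.

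In terms of SAP Table 2, the seven are all of ISS Stage II plus ISS Stage I with LDH >ULN.

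The 7 of 10 counts combinations, not patients, since the combinations are not equally common. For patients, affected number = N × (share with inconclusive iFISH) × (share of those in the seven combinations). N is about 300 (SAP section 1.3). Neither share is in the documents, so both are assumptions:

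- Low: 300 × 0.05 × 0.30 = 4.5, about 5.
- Middle: 300 × 0.10 × 0.50 = 15.
- High: 300 × 0.20 × 0.70 = 42.

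**The case against.** The strongest reply is that the effect is small and the consequences are easily overstated. Most of that stands.

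- A reader might infer that these patients vanish from the baseline table. They do not: Not classified is a category of its own, and section 2.1.1 also reports ISS stage, beta-2-microglobulin, albumin, LDH and cytogenetic risk (with an unknown/missing level). They also stay in the ISS subgroup, which needs no FISH.
- A reader might infer that the loss falls almost entirely on Stage II. It does not: 3 of the 10 unclassified combinations depend on iFISH and could be I or II, or II or III. Only the avoidable part of the loss is wholly Stage II.
- A reader might infer that rewording the row removes all distortion of the stage distribution. It does not, because no inconclusive patient could then be Stage I. As an illustration, with every input assumed: true stages I/II/III of 15/65/20%, 15% inconclusive at random, and 65% of Stage II and 60% of Stage III determinable. The current row keeps 15 × 0.85 = 12.75, 65 × 0.85 = 55.25 and 20 × (0.85 + 0.15 × 0.60) = 18.80, total 86.80, which is 14.7/63.7/21.7%. The reworded row keeps 12.75, 65 × (0.85 + 0.15 × 0.65) = 61.59 and 18.80, total 93.14, which is 13.7/66.1/20.2%. Each is off by up to about 1–2 points. The gain is in patients kept, not in an unbiased distribution.
- Local FISH reports may reduce the number inconclusive. Protocol section 1.2 collects qualifying ones for central review when central testing fails. SAP section 2.1.1 bases the cytogenetic abnormalities on central FISH assessment, so whether these reports feed R-ISS is unclear.
- Requiring a conclusive iFISH for every stage would be a defensible convention. The SAP has not adopted it, because it stages some patients as III without one. This reply therefore fails.

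**Conclusion.** The inconsistency is real and follows from Table 3 alone. A patient with inconclusive iFISH and beta-2-microglobulin 3.5 to <5.5 mg/L, or <3.5 mg/L with albumin <35 g/L or LDH >ULN, is Stage II by the table's own rules, yet is left unclassified. The count of about 5 to 42 of about 300 patients rests wholly on the assumed shares; the logical point does not.

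The reach is limited to one of the 15 factors in Table 9: its PFS subgroup and interaction test, the exploratory prognostic model in so far as unclassified patients are not given a level of their own, and any OS subgroup by R-ISS. The primary PFS comparison, the randomization strata and the ITT analysis do not use R-ISS. This is a minor correction.

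It would be tempting to conclude that the PFS subgroup already produced was wrong. The documents do not support that. SAP version 3 implements a protocol amendment that Table 1 places after the primary analysis, and Table 10 schedules PFS and study-entry characteristics (except gain(1q21)) at the primary analysis only. Which R-ISS rule applied then cannot be told.

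**What to change.** Reword the last row of Table 3 to: Not classified: inconclusive or missing iFISH, unless Stage II or III is determined by beta-2-microglobulin, albumin and LDH alone. Two patterns then stay unclassified: all Stage I laboratory conditions met, or beta-2-microglobulin ≥5.5 mg/L with LDH ≤ULN. The unclassified combinations fall from 10 to 3 of 12.

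Adding missing iFISH is a separate small change. Table 3 mentions only inconclusive results, although section 2.1.1 has an unknown/missing risk level, and the same logic holds for both.

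Also:

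- State which R-ISS rule the PFS subgroup at the primary analysis used, and label any re-staged subgroup as an update made after results were known.
- Report the Not classified count by arm beside the stages, because inconclusive patients can be staged II or III but never I.

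The cost is one table row, a re-run of the staging derivation from data already collected, and a sentence in the report. No new data are needed.
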